4 STUDY DESIGN

4.1 OVERALL DESIGN

A prospective, multicenter study that includes three key aims: 1) cross-sectional validation to define sensitivity and specificity of CAPTURE; 2) *qualitative* research exploration engaging clinical staff at all levels from primary care practices serving US patient populations of differing gender, racial, ethnic, urban/rural and socio-economic blends, and 3) explore the impact of CAPTURE on clinical care and patient outcomes across a broad range of primary care settings in a cluster randomized controlled clinical trial. The CAPTURE tool consists of a 5-item self-administered questionnaire and selected use of peak expiratory flow (PEF) measurement, designed to identify clinically significant Chronic Obstructive Pulmonary Disease (COPD).

For Aim 1, approximately 5,000 patients will be recruited at the time of their regularly-scheduled appointment across 100 participating primary care clinics associated with practice-based research networks (PBRNs). Eligible participants will undergo a baseline visit during which the CAPTURE tool and spirometry will be obtained, as well as PEF and other participant characteristics.

For Aim 2, approximately 150 clinicians from 10 participating primary care practices across 5 US PBRNs will undergo detailed implementation investigation of the CAPTURE case finding model for clinically significant COPD. In addition, 200 primary care patients recruited as part of Aim 1 will complete a 10- NIH-FDA Clinical Trial Protocol Template – v1.0 7 Apr 2017

minute written CAPTURE opinion survey.

To address Aim 3, participating primary care practices will be randomized in a 1:1 fashion to one of the following interventions:

- Arm 1: Practice clinicians will receive basic COPD education, and patient-level CAPTURE information with CAPTURE interpretation education (CAPTURE+ COPD education). As the second aim addresses the optimal format for delivering practice CAPTURE education this will be incorporated at the sites randomized to this arm (see Enhanced CAPTURE education in Figure 1).
- Arm 2: Practice clinicians will receive basic COPD education only (COPD education).

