9.1.1.1 SENSITIVITY AND SPECIFICITY OF THE CAPTURE TOOL

Primary Hypothesis 1. The CAPTURE tool will exhibit excellent sensitivity and specificity in diagnosing clinically significant COPD as defined by post-bronchodilator FEV₁/FVC < 0.70 in addition to either ≥1 exacerbation-like event (ECOPD) within the past 12 months or an FEV₁ < 60% predicted. Approximately 5000 patients will be enrolled in the study with the expectation that 300-800 of these will have previously undiagnosed clinically significant COPD, identified through research spirometry and documentation of prior respiratory events. Amongst cases, we will calculate the proportion of individuals who are at high risk for clinically significant COPD based on CAPTURE (sensitivity). Similarly, amongst non-cases, we will calculate the proportion of individuals not classified as having clinically significant COPD based on CAPTURE (specificity). Corresponding 95% confidence intervals will be calculated.

Based on our preliminary data drawn from a research setting, we noted 89.7% sensitivity and 93.1% specificity for CAPTURE. Table 9-1 shows the range of sensitivity and specificity 95% confidence interval widths that would result if the true sensitivity or specificity is 85%, 90% or 95% across a range of sample sizes. For instance, if we find 500 individuals with confirmed clinically significant COPD and CAPTURE has 90% sensitivity, then the 95% confidence interval for sensitivity would be 90% ± 2.6%. Similarly, if 4,000 individuals are confirmed to have no evidence of clinically significant COPD and CAPTURE has 90% specificity, then the 95% confidence interval for specificity would be 90% ± 0.9%.

| | | Sensitivity or Specificity | | |
|-------------|--|----------------------------|--------|--------|
| Sample Size | | 85% | 90% | 95% |
| 5000 | | ± 1.0% | ± 0.8% | ± 0.6% |
| 4000 | | ± 1.1% | ± 0.9% | ± 0.7% |
| 1000 | | ± 2.2% | ± 1.9% | ± 1.4% |
| 500 | | ± 3.1% | ± 2.6% | ± 1.9% |
| 250 | | ± 4.4% | ± 3.7% | ± 2.7% |
| 100 | | ± 7.0% | ± 5.9% | ± 4.3% |
| 50 | | ± 9.9% | ± 8.3% | ± 6.0% |

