Primary Hypothesis 3: *Sites where basic COPD and CAPTURE education are provided to clinicians, along with patient level CAPTURE data, will have a higher probability than control sites (i.e., those receiving only basic COPD education) of meeting the composite endpoint in their CAPTURE+ patients within 12 months of baseline.* From medical record review and follow-up patient survey responses, the composite endpoint is met if one of the following is recorded: (1) referral for or completion of clinical spirometry testing, 2) new clinical diagnosis of COPD, 3) newly prescribed respiratory medication (long acting bronchodilator or anti-inflammatory for respiratory condition), 4) referral to a specialist for respiratory evaluation/ treatment, or 5) referral for or completion of pulmonary rehabilitation.

The study will enroll 50 CAPTURE practices and 50 control practices; each practice will enroll 50 patients (for a total of approximately 5,000 patients). We project that within each practice, there will be at least 5 patients previously undiagnosed with COPD who have a CAPTURE+ screening result. The primary analysis will be to compare the average proportion of CAPTURE+ patients per practice that meet the composite endpoint in the two intervention arms. For power and sample sizes computations, this is a cluster randomized trial of n=50 clusters (practices) per intervention arm with 5 CAPTURE+ patients per cluster (practice). The primary power calculation is based on comparing the average cluster sample proportion (average proportion of CAPTURE+ patients per practice meeting composite endpoint) between intervention arms. Table 9-2 displays power for a two-sample test comparing average cluster sample proportions, accounting for possible intra-cluster correlation coefficient (ICC) values of 0.05, 0.10 and 0.15 that are typically seen in cluster randomized trials of behavioral interventions (<https://www.abdn.ac.uk/hsru/research/research-tools/study-design/>). These calculations assume a type I error of 5% and that the control arm meets the composite endpoint in 5% of CAPTURE+ patients and the CAPTURE arm meets the composite endpoint in higher percentages (columns of Table 9-2). There will be variability in the actual number of CAPTURE+ patients per practice. It is standard practice to inflate the number of needed clusters by 12% to account for this extra source of variability. Therefore, our power calculations are based on 44 clusters per intervention arm.

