9.3 STATISTICAL ANALYSES

9.3.1 SENSITIVITY AND SPECIFICITY (AIM 1)

SAS version 9.4 PROC LOGISTIC will be used for computations. Calculations of sensitivity and specificity along with their corresponding 95% confidence intervals assume independent Bernoulli outcomes for each patient. Clinically significant COPD+ and COPD- populations selected for these analyses are described in Section 9.2. CAPTURE+ patients are those with a baseline CAPTURE score ≥ 5 or with a baseline CAPTURE score of 2, 3, or 4 with a low PEF (defined as <350 L/min for males, <250 L/min for females).

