In addition to the primary sensitivity/specificity calculations, sensitivity/specificity and associated 95% confidence intervals will be calculated in predefined subgroups: sex, ethnic subgroups, rural and urban location, and educational status. As part of secondary analyses, receiver operating characteristic (ROC) curve analyses will evaluate different thresholds of the CAPTURE questionnaire score in defining a positive clinically significant + COPD screen, separately and in combination with low PEF characteristics, **and the additional CAPTURE questions**. As part of this exploration, participant and practice level data as well as interactions with the CAPTURE tool results, will be considered as predictors of clinically significant COPD using multivariable logistic regression. Corresponding positive and negative predictive values will be estimated across the range of prevalence percentages seen at the enrolled practices. Model selection in secondary logistic regression analyses will be based on forward selection using maximum likelihood theory, with entry into the model dependent on statistical significance at the 0.05 level. Exploration of this nature has the potential to produce artificially high operating characteristics (area under the curve [AUC], sensitivity and specificity) based on overfitting the data. SAS 9.4 PROC LOGISTIC includes a cross-validation approach to ROC curve analysis [ROCOPTIONS(CROSSVALIDATE)] that we will use when assessing operating characteristics for any new prediction tool that goes beyond the original CAPTURE metric considered in primary analyses. Once a final logistic regression model has been selected, classification thresholds for predicting clinically significant COPD will be described by the investigative team from the cross-validated ROC curve. Calibration plots of observed versus predicted sensitivity, and observed versus predicted specificity, will be conducted across previously specified subgroups of interest (sex, ethnic subgroups, rural and urban location, and educational status).

All of the above analyses will be applied to these additional populations: (1) patients with spirometrically defined COPD and (2) patients with mild COPD.

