9.3.2 PRACTICE BEHAVIOR (AIM 3)

The primary analysis of the Aim 3 primary endpoint will be to compare the average cluster sample proportion (average proportion of CAPTURE+ patients per practice meeting composite endpoint) between intervention arms. Practices that do not identify any CAPTURE+ subjects will not contribute to the primary analysis. The primary analysis is a two-sample test comparing average cluster sample proportions that explicitly takes into account correlation between individuals treated within the same practice. A two-sided p-value < 0.05 will be considered statistically significant. This analysis corresponds to a generalized estimating equation (GEE) regression analysis with (1) individual-level binary composite outcome data, (2) CAPTURE intervention group as a covariate, (3) practice id used to identify correlated outcomes, (4) exchangeable correlation matrix that assumes similar correlation between all composite outcome results for patients within the same practice, and (5) an identity link function so that the coefficient parameter corresponding to CAPTURE intervention group represents a difference in outcome probability. The primary analysis would then correspond to a test for whether the CAPTURE intervention group parameter is non-zero. There are no planned interim analyses for the primary endpoint, the rationale being that this is not a pharmaceutical or device trial that would benefit from standard stopping rules for efficacy. A DSMB will be monitoring the study for safety and study integrity.

Secondary analyses on meeting the composite outcome for participants who are CAPTURE+ will employ the GEE analysis framework with individual and practice level predictors in addition to the CAPTURE intervention group. Interactions will be assessed. We will also use the GEE framework to study and describe each of the individual components of the composite outcome as they relate to individual and practice level outcomes. In the subset of smoking patients, we will use GEE regression analysis to study additional binary outcomes, such as incidence of physician counselling/recommendation to stop smoking, physician referral to a formal smoking cessation program, newly prescribed smoking cessation medication, and referral to a smoking quit line.

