4.1 Preface

This Statistical Analysis Plan (SAP) describes statistical methods and analyses for the CAPTURE (COPD Assessment in Primary Care To Identify Undiagnosed Respiratory Disease and Exacerbation Risk) study, with emphasis on methods and analyses for the clinical trial component (Aim 3) of the CAPTURE Study Protocol version 7.0, dated June 25, 2023. This document should be read in tandem with the CAPTURE Study Protocol. When mentioned, CAPTURE Study Protocol Aim 1 and Aim 2 goals and analyses are grayed out in this document because they are out of scope of this SAP.

Chronic obstructive pulmonary disease (COPD) is the fourth leading cause of death in the US and a major cause of morbidity, mortality and health care expenditures. In primary care settings, the primary contact point for individuals seeking health care, COPD is often under diagnosed and associated opportunities for correct disease management are missed. The CAPTURE tool was developed to identify individuals

with undiagnosed COPD, and preliminary data has shown high sensitivity and specificity towards this goal. However, its use in primary care settings, where its potential impact on improved health care utilization is high, has not yet been studied.

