6.1 General Study Design and Plan

Overview: This is a prospective multi-PBRN, cluster randomized clinical trial to assess the operating characteristics of the CAPTURE COPD screening approach and compare respiratory related clinical actions and patient health status during the year following clinician receipt vs non-receipt of the CAPTURE results. Figure 1 provides a summary of the details of the study flow and data collection.

PBRNs: Seven PBRNs were selected from a pool of PBRNs with prior experience in large scale clinical trials. The selection process included surveying each candidate PBRN, reviewing survey responses and conducting telephone interviews with the director of each of those PBRNs. The final seven were selected based on interest, availability, prior experience in respiratory related clinical trials, geographic spread, socioeconomic, and racial/ethnic diversity of patients within the PBRN practices as well as willingness to participate in a five-year trial. These PBRNs were to enroll (collectively) 100 practices with 50 enrolled patients per practice completing spirometry and other study entry materials.

Practices and Clinicians: Each PBRN identified and enrolled practices based on interest and availability of space to complete the research visit within the practice building and willingness of the practice's clinicians to view the required educational modules. Enrolled practices were randomized in a 1:1 ratio to receive either basic COPD education or basic COPD education augmented with education on the CAPTURE Tool.

Patient Participants: Within each enrolled practice, potentially eligible patients of clinicians completing the required education are identified and invited to participate using one of two methods: (1) eligible patients identified by research and clinical staff are approached as they visit the clinic or (2) research staff are provided a list of patients with future appointments, and those aged 45-80 years are sent invitation letters by the PBRN to allow further contact and evaluation of eligibility and interest. The chosen method is based on prior PBRN experience and requirements of the local health systems and Institutional Review Boards (IRBs).

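### Aim 1's confidence intervals ignore clustering by practice, so the specificity interval is too narrow if CAPTURE results correlate within practice

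*Protocol*

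**What the plan says.** Protocol 4.1 describes a clustered sample for Aim 1: "approximately 5,000 patients will be recruited at the time of their regularly-scheduled appointment across 100 participating primary care clinics". Protocol 9.1.1.3 plans 50 patients per practice.

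For the primary Aim 1 estimates, Protocol 9.3.1 names PROC LOGISTIC and states: "Calculations of sensitivity and specificity along with their corresponding 95% confidence intervals assume independent Bernoulli outcomes for each patient". The planning section (9.1.1.1) follows the same approach. For 4,000 non-cases and a true specificity of 90%, it says "then the 95% confidence interval for specificity would be 90% ± 0.9"%.

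Aim 3 uses the same practices, and there the protocol treats clustering differently. The primary comparison in 9.3.2 "explicitly takes into account correlation between individuals treated within the same practice", and the power table in 9.1.1.3 is built "accounting for possible intra-cluster correlation coefficient (ICC) values of 0.05, 0.10 and 0.15".

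The SAP does not fill the gap. Its preface says that "Aim 1 and Aim 2 goals and analyses are grayed out in this document because they are out of scope of this SAP". No ICC, design effect, cluster-robust variance or cluster-based sensitivity analysis is given for Aim 1 in either document.

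**The concern.** Sensitivity and specificity are the Aim 1 primary endpoints, and their 95% intervals are the only inference stated for them. A binomial interval has its nominal coverage only if patients in the same practice are no more alike in their CAPTURE result, given case status, than patients in different practices.

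The documents give reasons to doubt that:

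- Protocol 9.1.2.1 says sites were selected to differ in sex, racial and ethnic, and rural/urban mix.
- SAP 6.1 has local coordinators perform the procedures and calculate the score.
- SAP 7.6 has the site's recorded score and peak-flow call define CAPTURE status in its primary analyses, even where these disagree with the raw data. SAP 10.4 summarises scoring accuracy by practice. A coordinator's habits are therefore shared by that coordinator's patients.

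None of this fixes the size of the correlation, but it makes exactly zero an unlikely value. What is at stake is whether the headline specificity interval is honest. The rural and urban subgroup intervals in 9.3.1 share the problem: SAP 7.6 classifies location by practice ZIP code, so whole practices fall into one subgroup and the number of patients per cluster does not shrink.

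**Working it through.** **Inputs from the documents.** About 100 practices (Protocol 4.1). Worked examples of 4,000 non-cases and 500 cases at 90% (9.1.1.1). Projected ranges of 3,400–4,400 non-cases and 300–800 cases (Table 9-3).

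**Assumed input.** The ICC of the CAPTURE result within practice, taken as 0.005 to 0.05. The 0.05–0.15 in 9.1.1.3 concerns a clinician-action outcome and is not carried over as a known value for Aim 1.

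**Step 1: reproduce the plan's figures.** Half-width = 1.96 × √(p(1−p)/n).

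- Specificity: 1.96 × √(0.09/4000) = 0.93 points (stated 0.9).
- Sensitivity: 1.96 × √(0.09/500) = 2.63 points (stated 2.6).

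All 21 cells of Table 9-1 reproduce to the printed decimal, so the table contains no design effect.

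**Step 2: cluster sizes.** Non-cases: 4000/100 = 40 per practice (34–44 over the projected range). Cases: 500/100 = 5 per practice (3–8 over the range).

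**Step 3: effect of clustering on specificity.** With m patients per practice and equal practice sizes, the design effect is DE = 1 + (m−1) × ICC. The correct half-width is the planned one × √DE. The planned interval's actual coverage is 2Φ(1.96/√DE) − 1.

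For ICC 0.01: DE = 1 + 39 × 0.01 = 1.39; half-width = 0.93 × √1.39 = 1.10; coverage = 2Φ(1.96/1.179) − 1 = 90.4%.

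The second column translates the ICC into the between-practice SD of specificity, √(ICC × 0.9 × 0.1). The last column repeats the coverage calculation with half the ICC. That corresponds to the assumption that half of it lies between PBRNs treated as fixed strata.

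| Assumed ICC | SD of specificity (points) | DE | Half-width (planned ±0.93) | Coverage of planned interval | Coverage, half the ICC between fixed PBRNs |
|---|---|---|---|---|---|
| 0.005 | 2.1 | 1.195 | ±1.02 | 92.7% | 93.9% |
| 0.01 | 3.0 | 1.39 | ±1.10 | 90.4% | 92.7% |
| 0.02 | 4.2 | 1.78 | ±1.24 | 85.8% | 90.4% |
| 0.05 | 6.7 | 2.95 | ±1.60 | 74.6% | 83.7% |

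Without the PBRN split, coverage drops below 94% at an ICC of about 0.002 and below 90% at about 0.011. Over 3,400–4,400 non-cases it is 93.1–92.5% at ICC 0.005 and 91.1–89.9% at 0.01.

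**Step 4: sensitivity.** With m = 5, DE = 1 + 4 × 0.01 = 1.04 at ICC 0.01, so ±2.63 becomes ±2.68. At ICC 0.05, DE = 1.20, the half-width is ±2.88 and coverage is 92.6%.

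**Step 5: simulation check.** Beta-binomial data were generated for 100 practices of 40 non-cases at 90% specificity, with 20,000 runs. The planned interval covered 92.6%, 90.2%, 85.9% and 74.8% at the four ICCs, in line with the formula. A cluster-robust interval on the logit scale covered about 95% throughout, including with unequal practice sizes. At ICC 0 its half-width was ±0.93 to ±0.94, against ±0.93 planned.

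**The case against.** The strongest counter-argument concerns the target. The planned interval undercovers only if the practices stand for a wider population. If the target is pooled specificity in these particular practices, variation between them is not sampling error. The design effect is then 1 − ICC, and simulation puts the planned interval's coverage at about 95%. Practices were also not randomly sampled: "Each PBRN identified and enrolled practices based on interest and availability of space". This is correct as a statement about estimands, but it does not fit the trial. The Aim 1 objective speaks of primary care settings broadly, not of the enrolled clinics alone, and the protocol nowhere restricts inference to them.

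Second, the size is unknown. No document gives an ICC for the CAPTURE result, and an ICC of 0.05 implies a spread of about 7 points of specificity between practices. This stands. The lower rows of the table are scenarios, not predictions.

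Third, the consequence is modest: tenths of a point at small ICCs, no change in the estimates, and no decision rule that depends on the interval. The assumption is also stated openly, and 9.3.1 does look at heterogeneity through subgroups and practice-level predictors. All of this is true and limits the weight of the point. None of it corrects the overall interval.

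**Conclusion.** The concern holds. The plan applies an independence assumption to the Aim 1 primary intervals in a clustered sample, accounts for the same clusters in Aim 3, and corrects the Aim 1 intervals nowhere.

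For any positive within-practice correlation among non-cases, with practices viewed as a sample from a wider population, the specificity interval is too narrow. At ICCs of 0.005 to 0.01 the understatement is about 0.1 to 0.2 points of half-width (1.02 − 0.93 and 1.10 − 0.93), with coverage of 92.7% to 90.4%. It grows if the ICC is larger and shrinks if part of it lies between PBRNs treated as fixed. Equal practice sizes are assumed, and unequal sizes would raise the design effect somewhat.

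This should be fixed as a matter of interval validity. It does not threaten feasibility, the point estimates or, to any important degree, the sensitivity interval.

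**What to change.** In Protocol 9.3.1, replace the independence sentence with wording such as:

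> 95% confidence intervals for sensitivity and specificity will use a cluster-robust (sandwich) variance with practice as the cluster, from an intercept-only logistic GEE with independence working correlation (or a survey logistic model), back-transformed from the logit scale.

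With an independence working correlation the point estimate remains the pooled proportion. State whether PBRN is treated as a fixed stratum, and apply the same variance to the subgroup intervals. Report the estimated within-practice ICC, which will settle the question of size.

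A note under Table 9-1 should say that its half-widths assume no clustering, and should show the 4,000-non-case example over a range of assumed ICCs. One design effect should not be applied to every row, because cluster sizes differ between cases and non-cases. This note is the less important part, since it cannot affect recruitment now.

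The cost is one sentence and a table note. No new data are needed, because practice ID is already used in the Aim 3 model. The intervals will be slightly wider if clustering exists and practically unchanged if it does not.

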| OBJECTIVES | ENDPOINTS | JUSTIFICATION FOR ENDPOINTS |
|--|---|---|
| Aim 1: Determine patient and site characteristics that, with the CAPTURE assessment, will best identify persons with undiagnosed COPD. | AUC to identify the combination of patient/site characteristics which best discriminates those with clinically significant COPD. | The best discrimination will determine which site and patient characteristics best predicted undiagnosed COPD in combination with the CAPTURE tool. |
| Aim 1: Determine whether CAPTURE is useful in identifying other definitions of undiagnosed COPD: 1) spirometry-defined COPD, and 2) mild COPD | All primary and secondary endpoints as applied to 1) spirometry-defined COPD and 2) mild COPD | This will determine the robustness of the CAPTURE tool. |
| Aim 3: Define the impact of providing CAPTURE education and patient-level CAPTURE information to clinicians on selected clinician interventions for the management of CAPTURE+ patients. | Proportion of CAPTURE+ participants who have each of the following occur within 12 months of study baseline (separate endpoints to be evaluated individually): 1-5) each component of the Aim 3 primary endpoint, and 6) recommendation or administration of influenza vaccination. | Each endpoint is clinically relevant and consistent with published data. (45) This will test the impact of CAPTURE on clinician behavior. |
| Aim 3: Assess the impact of CAPTURE education and patient-level CAPTURE information on clinician interventions specific to smokers who are CAPTURE+. | Proportion of CAPTURE+ participants currently smoking at the baseline study visit who have any of the components of the Aim 3 primary endpoint or any of the following occur within 12 months of baseline (evaluated as a composite endpoint and as individual endpoints): 1) clinician counseling or recommendation for smoking cessation, 2) referral to a smoking cessation program, 3) referral to a smoking quit line, and 4) newly prescribed medication for smoking cessation. | Certain outcomes are specific to only smokers and should be assessed. |
| OBJECTIVES | ENDPOINTS | JUSTIFICATION FOR ENDPOINTS |

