For each Aim 3 outcome that is collected via both medical record review and patient survey, the primary analysis will be among patients with complete outcome data from both the medical record and patient survey. Sensitivity analyses will be conducted by imputing missing outcome data using different assumptions and applying the primary analysis method to the resulting data sets. Sensitivity analyses will include (1) imputation of negative responses (i.e., responses indicating that the outcome has not occurred) for all missing patient survey responses, followed by analysis of all patients with medical record review data; (2) imputation of positive responses (i.e., responses indicating that the outcome has occurred) for all missing patient survey responses, followed by analysis of all patients with medical record review data; and (3) multiple imputation of all missing outcome data using the observed outcomes and covariates, followed by analysis of all patients selected for follow-up.

In participants who are CAPTURE+, change in CAT score will be analyzed using mixed models with a random effect for practice. The average cluster sample proportion of patients who experience exacerbations will be compared between intervention groups using methodology similar to that used for the primary endpoint. Subject to having sufficient mortality events, survival analysis allowing for correlation of endpoints within cluster (practice) will be used to compare mortality between

intervention groups and perform multivariable analysis. We will explore differences between intervention groups in the average cluster sample rate of hospitalizations again using GEE. All additional secondary analyses will also be applied to patients with clinically significant and spirometrically defined COPD, Mild COPD, PRISM, and symptomatic non-obstruction. Practices that do not have any patients with these conditions will not contribute to analyses of these secondary endpoints, respectively.

Model selection in GEE secondary analyses will be based on statistical significance at the 0.05 level using robust sandwich estimation of variability within clusters. Model fit will be checked by comparing observed versus predicted values within predefined subgroups of interest (sex, ethnic subgroups, rural and urban location, and educational status).

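### Aim 1 selects practice-level predictors of COPD with tests that ignore practice clustering, so unrelated practice characteristics can enter the model more often than the stated 5%

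*Protocol*

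**What the plan says.** Finding the site characteristics that help identify undiagnosed COPD is a named Aim 1 secondary objective. The justification in Protocol section 3 reads: "The best discrimination will determine which site and patient characteristics best predicted undiagnosed COPD".

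Section 9.3.1 gives the method. In a multivariable logistic regression, "participant and practice level data as well as interactions with the CAPTURE tool results, will be considered as predictors of clinically significant COPD". The selection rule is: "Model selection in secondary logistic regression analyses will be based on forward selection using maximum likelihood theory". A term is admitted if its test gives p below 0.05. On software, the section says "SAS version 9.4 PROC LOGISTIC will be used for computations". It also says that the sensitivity and specificity calculations "assume independent Bernoulli outcomes for each patient". It names no GEE, random practice effect or robust variance for the prediction model.

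Section 9.3.2 differs. Model selection for Aim 3, in the same practices and also at the 0.05 level, uses "robust sandwich estimation of variability within clusters".

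The SAP (4.1) places Aim 1 outside its scope, so it neither repeats nor corrects the Aim 1 rule.

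**The concern.** The null hypothesis for a practice-level term is that the characteristic is unrelated to COPD risk. An ordinary likelihood test also assumes that, given the model terms, patients in the same practice are independent. If practices differ in COPD risk for reasons the model does not contain, the test can reject because practices differ, not because the characteristic matters.

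Aim 1 is where practice characteristics are themselves the question, yet it lacks the protection the protocol gives Aim 3. At stake is the answer to one secondary objective. Spurious site terms would describe these 100 practices and would not carry over to others. The selected model also feeds the cross-validated ROC curve from which classification thresholds are to be read, and the work is repeated for spirometric and mild COPD.

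**Working it through.** **Inputs from the documents.** There are 100 practices of 50 patients (Protocol 9.1.1.3) and the entry level is 0.05 (9.3.1). Expected cases are 300 to 800 (9.1.1.1) and non-cases 3,400 to 4,400 (Table 9-3). Cases plus non-cases run from 800 + 3,400 = 4,200 to 300 + 4,400 = 4,700, or 42 to 47 per practice. Rural patients are 46% (Table 9-3), used here as the share of practices with an example characteristic.

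**Assumption.** The ICC of COPD status within practice, beyond the model terms, is not given. The only ICCs in the documents (0.05, 0.10 and 0.15) belong to the Aim 3 clinician-behaviour endpoint. A range of 0.005 to 0.05 is shown.

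**Step 1: reproduce the stated 5%.** With ICC = 0, 100 practices of 47 patients, 46 practices with the characteristic and prevalence of 6% or 16%, 20,000 simulated runs give a rejection rate of 5.0 to 5.1% for the likelihood-ratio and score tests. The stated level is right if there is no clustering.

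**Step 2: formula with clustering.** For a covariate constant within practices of size m, the design effect is DE = 1 + (m − 1) × ICC. The true entry rate of an unrelated covariate is 2 × [1 − Φ(1.96/√DE)].

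For m = 50:
- ICC 0.01: DE = 1 + 49 × 0.01 = 1.49; 1.96/√1.49 = 1.606; rate 10.8%.
- ICC 0.05: DE = 1 + 49 × 0.05 = 3.45; 1.96/√3.45 = 1.055; rate 29.1%.

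| ICC (assumed) | m = 42 | m = 47 | m = 50 |
|---|---|---|---|
| 0 | 5.0% | 5.0% | 5.0% |
| 0.005 | 7.4% | 7.7% | 7.9% |
| 0.01 | 9.9% | 10.5% | 10.8% |
| 0.02 | 14.6% | 15.7% | 16.4% |
| 0.05 | 26.2% | 28.1% | 29.1% |

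**Step 3: simulation check.** Beta-binomial data with m = 47 give 10.5% at ICC 0.01 and 28% at 0.05, at both prevalences. With practice sizes varying (coefficient of variation 0.4), the rates rise slightly, to about 11.5% and 31%.

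**Step 4: CAPTURE already in the model.** Random-intercept logistic data give 9.7% at an ICC of about 0.009, 16.4% at about 0.021 and 27% at about 0.040. In the same runs the practice-by-CAPTURE interaction test rejects 4.5 to 6.0% of the time, which is not inflated.

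**Step 5: how much clustering doubles the rate.** A true rate of 10% needs DE = (1.96/1.645)² = 1.42, so ICC = 0.42/49 = 0.0086. At 6% prevalence, an ICC of 0.009 is a between-practice standard deviation in true risk of √(0.009 × 0.06 × 0.94), about 2.3 percentage points.

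**Step 6: the clustered test.** A sandwich test by practice holds 4.8 to 5.5% for ICCs from 0 to 0.15, and 4.6 to 6.0% with CAPTURE in the model. If only 20% of practices have the characteristic, it rejects 5 to 8% of the time.

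**The case against.** The strongest reply is that this is labelled exploratory work with discrimination, not p-values, as its endpoint. Section 9.3.1 warns of overfitting and requires cross-validated ROC curves and calibration by subgroup, including rural and urban location. A rough forward-selection simulation with five unrelated practice factors (250 runs per setting, covariate effects assumed) put the mean AUC loss in new practices at only 0.003, 0.004 and 0.009 for ICCs of about 0.009, 0.02 and 0.06, against 0.001 with no clustering. That stands as a limit on the harm. It does not repair the entry rule: cross-validating the ROC curve leaves the test unchanged, and the text does not say that practices are held out whole. The objective also asks which site characteristics matter, and AUC alone does not answer that.

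Several stronger readings are tempting but unsupported:

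- **A fixed inflation of two to six times.** This holds only for an ICC of about 0.009 to 0.053 at 50 patients per practice. No document gives that ICC, and patient-level terms may lower the residual value.
- **That the protocol itself expects excess variation.** Section 9.3.1 plans predictive values over the prevalences found across practices. With about two spirometric COPD patients per practice (SAP 13.1), observed prevalence would vary widely by chance and by patient mix.
- **That the independence statement covers the selection model.** It is written for sensitivity and specificity. Independence in the selection model is inferred from the maximum-likelihood wording, the software and the contrast with 9.3.2.
- **A 48 to 90% chance that some spurious practice term enters.** Such figures arise from five practice variables in SAP 9.4 at ICCs of 0.01 to 0.05. That list belongs to Aim 3, Aim 1 does not name its practice-level candidates, and 23% is ordinary multiplicity with no clustering at all.

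**Conclusion.** The concern holds, conditionally and for practice-level main effects only. As written, the Aim 1 entry test is anti-conservative whenever COPD risk varies between practices beyond the model terms. With about 50 patients per practice and an assumed residual ICC of 0.01 to 0.05, an unrelated practice characteristic tested on its own would enter about 10 to 29% of the time rather than 5%; at 0.005 the figure is about 8%. The true ICC is unknown until it is estimated from the baseline data.

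No inflation was shown for practice-by-CAPTURE interactions, although the check used a random intercept only, so it does not cover a CAPTURE effect that itself differs between practices. Inflation for patient-level predictors is likewise not shown. The primary sensitivity and specificity estimates do not depend on this model. The point is worth correcting because the remedy is cheap and the protocol already applies it to Aim 3.

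**What to change.** In Protocol 9.3.1, base entry of practice-level main effects on a GEE logistic model with practice as the cluster and robust variance, as in 9.3.2, or on a logistic model with a random practice intercept. State that any new tool containing practice-level terms will be cross-validated by leaving out whole practices, so that those terms are judged in practices not used to fit them. Reporting the estimated ICC of COPD status would let readers see how much the change mattered.

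The cost is a wording change, a different SAS procedure and slightly more analysis work, with no new data. Fewer practice-level terms will be retained. Robust tests may also be mildly liberal (5 to 8%) when few practices have the characteristic.
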